2.3.2. Conclusion

The magnitude of diabetes in youth in the U. S. is not known and precise estimates in many ethnic groups are not available. Furthermore, the magnitude of diabetes by type is also not clear except in a few selected groups. A major challenge is to develop better methods of classifying types of diabetes. In addition, the burden of disease and the

frequency and impact of microvascular complications, cardiovascular risk factors, and macrovascular complications in pediatric diabetes are not known. Similarly, the extent of implementation of the processes of care and available treatments is unclear.

To address these issues, SEARCH, a multi-center collaborative 5-year study of diabetes in youth aged <20 years in the United States was established. SEARCH will recruit approximately 6,000 prevalent cases across these sites and establish a registry system to identify an estimated 800 incident cases per year. The study will use a uniform population-based approach using a common protocol developed by study investigator consensus.

Table 2 -1. Selected current estimates of the magnitude of type 2 diabetes in North American children and adolescents, in population- and clinic-based studies and case series⁵.

STUDY AND REFERENCE*	YEARS	RACE/ETHNICITY	AGE (YEARS)	SAMPLE SIZE	NUMBER OF CASES	ESTIMATES
						Prevalence per 1,000 and 95 % confidence interval
• Population-based studies						
- New Mexico	1991-1992	Navajo Indians	12-19	142	2 [†]	14.1 [0–33.5] [†]
- Arizona	1992-1996	Pima Indians	10-14	672	15	22.3 [11.1–33.5]
			15-19	530	27	50.9 [32.2-69.6]
- Manitoba	1996-1997	Cree and Ojibway Indians	4-19	717	8	11.1 [3.4-18.8]
			10-19	-	7	0 for boys and 36.0 for girls
- NHANES III	1988-1994	Whites, and African and Mexican Americans, all U.S.	12-19	2,867	13 [†]	4.1 [0-8.6] [†]
• Clinic-based studies						
- Indian Health Services	1996	American Indians, all U.S.	0-14	402,580	518 [†]	1.3 [†]
			15-19	111,239	498 [†]	4.5 [†]
- Manitoba	1998	Cree and Ojibway Indians	5-14	20,900	20	1.0
			15-19	8,400	19	2.3
						Incidence per 100,000/year
- Cincinnati, OH	1994	Whites and African Americans	0-19	-	-	3.5
			10-19	-	-	7.2

STUDY AND REFERENCE*	YEARS	RACE/ETHNICITY	AGE (YEARS)	SAMPLE SIZE	NUMBER OF CASES	ESTIMATES
• Case series				‡		% of type 2 diabetes among new cases of diabetes
- Cincinnati, OH	1982-1994	Whites and African Americans	0-19	1,027§	54§	16§ (in 1994)
			10-19	-	-	33§ (in 1994)

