- Charleston, SC	1997	African Americans	10-19	97	45	46
- Little Rock, AK	1988-1995	Whites, Hispanics, and African Americans	0-19	-	50	-
- San Diego, CA	1993-1994	Whites, Hispanics, and African and Asian Americans	0-16	160§	13§	8§
- San Antonio, TX	1990-1997	Whites, Hispanics	-	560§	101§	18§
- Ventura, CA	1990-1994	Hispanics	0-17	31§	14§	45§

† Estimates include cases of type 1 diabetes.

‡ In case series, the sample size refers to the total number of cases of diabetes (type 1 and 2).

§ Incident cases.

Note: numbers in italics are estimates. – corresponds to unknown data.

Table 2 - 2. Characteristics of 578 North American children and adolescents at diagnosis of type 2 diabetes⁵

CHARACTERISTICS		STUDY REFERENCE* AND SAMPLE SIZE									
		Cincinnati OH (ref 14) n=54	Charleston NC (ref 15) n=39	Little Rock AK (ref 17) n=50	San Diego CA (ref 19) n=18	San Antonio TX (ref 20) n=101	Ventura CA (ref 21) n=21	Chicago IL (ref 28) n=160	Sioux Lookout Zone Ontario (ref 9) n=15	Manitoba (ref 5) n=20	Gila River AZ† (ref 12) n=100
Ethnicity (%)	African American	69	100	74	11	-		75			
	Hispanic			2	67	83	100	25			
	White	31		24	17	-					
	American Indian				‡				100	100	100
Female:male ratio	1.7	1.3	1.6	2.0	3.0	0.8	1.7	1.4	4.0	1.7	
Family history (%)1 st or 2 nd degree		85	95	-	87	74	100	-	93	100	-
	1 st degree relative	65	72	-	80	45	>60	50	69	100	-
Mean age (years)	14	13	14	13	13	14	14	12	12	16	
Youngest age (years)	8	7	8	5	6	10	-	7	7	4	
Mean BMI (kg/m ²)	38	30	35	27	-	33	33	29	26	35	
Acanthosis nigricans (%)	60	56	86	67	92	-	-	-	-	-	
Presence of weight loss (%)	19-100	31§	40	-	50	-	62	30	0	-	
Mean HbA1C (%)	-	12	11	-	-	10	-	13	13	6	
Ketosis (%)	-	79§	16-18	33	-	33	-	50	25	-	

CHARACTERISTICS	STUDY REFERENCE* AND SAMPLE SIZE									
Ketoacidosis (%)	-	46§	>25	14	-	5	52	-	-	-
Diagnosis due to (%) Symptoms	66	-	-	-	-	86	-	100	25	-
Screening	2**	-	-	-	-	14**	-	0	-	100
Urinalysis	32	-	-	-	-	-	-	0	75	-

* Numbered references may be found in reference list. Numbers of cases may differ from those reported in table 1 due to missing data for some cases or inclusion of additional cases from satellite-clinics.

† This case series included youth diagnosed by systematic screening between 1965 and 1998.

‡ One Cambodian case.

§ History of weight loss, ketosis or keto-acidosis.

** Evaluation for obesity or strong family history of diabetes.

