4.1.2. Denominators for prevalence

The following tables summarize projections from Census 2000 data on July 1, 2001 for the 8-county primary service area of CCHMC. A race-bridging model and zip code level geocoding were used to arrive at the race/ethnicity specific totals.

Characteristic	Population Denominators (%)
Total population	549,356
Age group	
0 – 4 years	132,995
5 – 9 years	135,708
10 – 14 years	143,334
15 – 19 years	137,319

Gender	
Male	280,744
Female	268,612
Race/ethnicity	
Non-Hispanic White	445,009
African-American	86,296
Hispanic	8,204
Asian/Pacific Islander	8,659
American Indian	1,188

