Seattle	16.7	380465	63	13.1	29337	3	11.4	24479	2	3.2	37947	1	14	9487	1	0	8195	0	70
S Carolina	16.7	341223	56	13.1	214334	28	11.4	16134	1	3.2	4966	0	14	202	0	0	2117	0	85
Total		3284466	489		672587	71		549501	46		301875	5		89162	10		175397	0	621

Table V – 5. Estimated Annual Number of Incident Cases Type 2

Age	Non-Hispanic White			African American			Hispanic			Asian			Pacific Islander			Native American			ALL
	Rate	Denom	N	Rate	Denom	N	Rate	Denom	N	Rate	Denom	N	Rate	Denom	N	Rate	Denom	N	
0 thru 9																			
California	0.7	170740	1	5	32621	1	1.8	100294	1	2.07	28997	0	3.3	7249	0	4.7	1742	0	3
Colorado	0.7	504413	3	5	32685	1	1.8	121224	2	2.07	14948	0	3.3	725	0	4.7	74453	3	9
Hawaii	0.7	32869	0	5	4137	0	1.8	17166	0	2.07	63443	1	5	26143	1	4.7	399	0	2
Ohio	0.7	235,458	1	5	31,556	1	1.8	0	0	2.07	0	0	3.3	0	0	4.7	0	0	2
Seattle	0.7	383,387	2	5	32446	1	1.8	26367	0	2.07	34422	0	3.3	8605	0	4.7	7783	0	3
S Carolina	0.7	319645	2	5	195522	9	1.8	17146	0	2.07	4727	0	3.3	173	0	4.7	1833	0	11
10 thru 19																			
California	2.9	179361	5	7.2	34269	2	9.5	105359	10	13.9	30461	4	11.3	7615	0	21.3	1742	0	21
Colorado	2.9	451376	13	7.2	27703	1	9.5	102736	9	13.9	13234	1	11.3	642	0	21.3	76700	16	40
Hawaii	2.9	35608	1	7.2	4482	0	9.5	18596	1	13.9	68730	9	22	28321	6	21.3	433	0	17
Ohio	2.9	249,921	7	7.2	33,495	2	9.5	0	0	13.9	0	0	11.3	0	0	21.3	0	0	9
Seattle	2.9	380465	11	7.2	29337	2	9.5	24479	2	13.9	37947	5	11.3	9487	1	21.3	8195	1	22
S Carolina	2.9	341223	9	7.2	214334	15	9.5	16134	1	13.9	4966	0	11.3	202	0	21.3	2117	0	25
Total		3284466	55		672587	35		549501	26		301875	20		89162	8		175397	20	164

Estimated Incident Cases	
	TOTAL
California	103
Colorado	217
Hawaii	42
Ohio	89
Seattle	151
S Carolina	183
	785
Rates are per 100,000	

Table V – 6. Estimated Annual Number of Incident Cases All Types

Age	Non-Hispanic White			African American			Hispanic			Asian			Pacific Islander			Native American			ALL
	Rate	Denom	N	Rate	Denom	N	Rate	Denom	N	Rate	Denom	N	Rate	Denom	N	Rate	Denom	N	
0 thru 9																			
California	0.7	170740	24	5	32621	4	1.8	100294	8	2.07	28997	0	3.3	7249	0	4.7	1742	0	36
Colorado	0.7	504413	71	5	32685	4	1.8	121224	10	2.07	14948	0	3.3	725	0	4.7	74453	3	88
Hawaii	0.7	32869	4	5	4137	0	1.8	17166	1	2.07	63443	3	5	26143	4	4.7	399	0	12
Ohio	0.7	235,458	32	5	31,556	3	1.8	0	0	2.07	0	0	3.3	0	0	4.7	0	0	35
Seattle	0.7	383,387	53	5	32446	4	1.8	26367	1	2.07	34422	0	3.3	8605	1	4.7	7783	0	59

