S Carolina	0.7	319645	45	5	195522	27	1.8	17146	1	2.07	4727	0	3.3	173	0	4.7	1833	0	73
10 thru 19																			
California	2.9	179361	34	7.2	34269	6	9.5	105359	22	13.9	30461	4	11.3	7615	1	21.3	1742	0	67
Colorado	2.9	451376	88	7.2	27703	4	9.5	102736	20	13.9	13234	1	11.3	642	0	21.3	76700	16	129
Hawaii	2.9	35608	6	7.2	4482	0	9.5	18596	3	13.9	68730	11	22	28321	10	21.3	433	0	30
Ohio	2.9	249,921	48	7.2	33,495	6	9.5	0	0	13.9	0	0	11.3	0	0	21.3	0	0	54
Seattle	2.9	380465	74	7.2	29337	5	9.5	24479	4	13.9	37947	6	11.3	9487	2	21.3	8195	1	92
S Carolina	2.9	341223	65	7.2	214334	43	9.5	16134	2	13.9	4966	0	11.3	202	0	21.3	2117	0	110
Total		3284466	544		672587	106		549501	72		301875	25		89162	18		175397	20	785

Table V - 7. Prevalence (per 1000) of Diabetes by Age, Type and Ethnicity: Rates Based on the Published Literature and Unpublished Data Available to SEARCH Investigators

	NHW	AA	Asian	PI	NA	Hispanic
Type 1						
Age 0-9	1.00	1.00	0.10	1.00	0.01	0.50
Age 10-19	2.20	2.20	0.80	2.50	0.01	1.80
Type 2						
Age 0-9	0.05	0.05	0.10	0.11	0.40	0.13
Age 10-19	0.39	1.18	0.78	1.07	1.70	1.46

NHW = non-Hispanic white, AA = African American, PI = Pacific Islander, NA = Native American

Table V – 8. Estimated Incidence (per 100,000 per year) of Diabetes by Age, Type and Ethnicity: Rates Based on the Published Literature and Unpublished Data Available to SEARCH Investigators

	NHW	AA	Asian	PI	NA	Hispanic
Type 1						
Age 0-9	13.5 ^a	9.5 ^c	0.9 ^h	12.7 ^j	0	7.0 ^a
Age 10-19	16.7 ^a	13.1 ^d	3.2 ^h	14.0 ^j	0	11.4 ^a
Type 2						
Age 0-9	0.7 ^b	5.0 ^c	2.07 ⁱ	3.3 ^k	4.7 ^g	1.8 ^b
Age 10-19	2.9 ^b	7.2 ^f	13.9 ⁱ	11.3 ^k	21.3 ^g	9.5 ^b

NHW = non-Hispanic white, AA = African American, PI = Pacific Islander, NA = Native American

^a using 1978-1988 Colorado incidence rates

^b estimated from ^a using type1/type 2 prevalence rates

^c estimated based on data from Libman et al. Diabetes Care 21:1278, 1998

^d estimated from ^f using type1/type2 prevalence rates

^e using S. Carolina Pilot registry data supplied by [name]

^f using data from Pinhas-Hamiel et al. J Pediatr 128: 608, 1996

^g using Pima Indian data from NIDDK, [name]

^h averaged using data from Asians in Hawaii (Patrick et al. Diabetes Care 20: 983, 1997) and from China and Japan (Karvonen et al. Diabetes Care 23:1516, 2000)

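### The African American type 2 incidence planned for ages 10-19 (7.2 per 100,000) matches a Cincinnati rate for whites and African Americans combined and conflicts with the protocol's own Cincinnati data, so expected cases look too low

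*Protocol*

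**What the plan says.** Section 4.2.2.4 says the expected incident counts serve to assess power and to plan resources. They are literature or unpublished rates applied to each center's denominators, with the rates in Appendix V.

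- **Table V-8**, type 2, non-Hispanic white then African American: "Age 10-19 2.9 ^b 7.2 ^f". Footnote f cites one publication, "J Pediatr 128: 608, 1996". Footnote b derives the white rate from Colorado type 1 incidence and the type 1/type 2 prevalence ratio. Footnote d derives the African American type 1 rate at 10-19 (13.1) from f in the same manner.
- **Table 2-1** (Section 2) has one type 2 incidence entry: "Cincinnati, OH 1994 Whites and African Americans 0-19 - - 3.5". Its next line, ages 10-19, gives 7.2. The same table puts type 2 at 33% of new Cincinnati cases at 10-19 in 1994.
- **Table 2-2**, Cincinnati being the first column: "African American 69 100 74". African Americans were 69% and whites 31% of 54 type 2 cases.
- **Table V-5**, ages 10-19: "Ohio 2.9 249,921 7 7.2 33,495 2", that is 7 white and 2 African American cases.
- **Table 6-2** (Section 8.2): 106 African American cases a year in 672,587, interval ±19.0%; 785 cases overall, ±7.0%.

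**The concern.** A combined rate for two groups lies between the two group rates. If 7.2 is the combined Cincinnati rate and whites are at 2.9, the African American rate must be well above 7.2. Table V-8 nevertheless gives 7.2 to African Americans alone.

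The figure carries weight. African American cells at ages 10-19 supply 64 of the 106 expected African American incident cases (22 type 2, 42 type 1), and through footnote d the type 1 cells rest on the same number. The results feed Tables V-4 to V-6, 4-3, 3-2 and 6-2. Incidence by type and ethnicity is part of primary aim (a).

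**Working it through.** **1. Reproduce the plan.** Cases = denominator × rate, truncated within center. African American denominators at 10-19 (Table V-10), in the order California, Colorado, Hawaii, Ohio, Seattle, South Carolina: 34,269 + 27,703 + 4,482 + 33,495 + 29,337 + 214,334 = 343,620.

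- Type 2 at 7.2: 2+1+0+2+2+15 = 22 (24.7 untruncated)
- Type 1 at 13.1: 4+3+0+4+3+28 = 42
- Ages 0-9: 13 type 2 and 29 type 1
- Total: 22+42+13+29 = 106, as printed
- Half-width ≈ 196/√N %: 196/√106 = 19.0% and 196/√785 = 7.0%, as printed

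The arithmetic is sound, so any fault lies in the input.

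**2. Compare planned Ohio with reported Cincinnati.**

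| Check | Planned | Reported |
|---|---|---|
| Type 2 cases, 10-19, in 283,416 youth | 9 (9.7 untruncated) | 283,416 × 7.2/100,000 = 20.4 |
| Type 2 rate, 10-19, per 100,000 | 3.2 (3.4 untruncated) | 7.2 |
| Type 2 share of cases, 10-19 | 9/54 = 17% | 33% |
| African American share of type 2 cases | 3/11 = 27% | 69% |

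None of these comparisons needs footnote f to be the Cincinnati series.

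**3. African American population share in Cincinnati.**

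- Table V-10, ages 10-19: 33,495/283,416 = 11.8%
- Cincinnati site section 4.1.2, ages 0-19 ("African-American 86,296" against 445,009 whites): 86,296/531,305 = 16.2%

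**4. Rate needed if whites stay at 2.9.**

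- (7.2 − 2.9 × 0.838)/0.162 ≈ 29
- (7.2 − 2.9 × 0.882)/0.118 ≈ 39

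**5. Rate from the 69%/31% case mix** (combined rate × case share / population share).

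- 16.2% share: 7.2 × 0.69/0.162 ≈ 31; whites 7.2 × 0.31/0.838 ≈ 2.7
- 11.8% share: 7.2 × 0.69/0.118 ≈ 42; whites 7.2 × 0.31/0.882 ≈ 2.5

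The implied white rate is close to the planned 2.9, so it is the African American entry that does not fit.

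**6. Carry the step 5 rates forward**, replacing only the 22 type 2 cases and holding type 1 at 13.1.

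| Per year | Plan | At about 31 | At about 42 |
|---|---|---|---|
| African American type 2, 10-19 | 22 | 102 | 142 |
| of which South Carolina | 15 | 65 | 90 |
| All African American | 106 | 84+102 = 186 | 84+142 = 226 |
| Half-width | 19.0% | 14.4% | 13.0% |
| All type 2 | 164 | 142+102 = 244 | 142+142 = 284 |
| All cases | 785 | 763+102 = 865 | 763+142 = 905 |
| Overall half-width | 7.0% | 6.7% | 6.5% |

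South Carolina holds 214,334/343,620 = 62% of the affected denominator.

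**7. Sensitivity and type 1.** Case shares of 60-75% give rates of about 27-46 and African American totals of about 173-238. Footnote d's link is visible: 7.2 × 2.20/1.18 = 13.4, near the printed 13.1. Rescaling type 1 the same way from 31-42 would give about 57-78 per 100,000, far above the 30.4 that Section 2.2.1 quotes for African Americans aged 15-19 in Allegheny County.

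**The case against.** **Is 7.2 shown to be the combined Cincinnati rate, miscopied?** A reader might infer so from the identical figure and age band. The protocol does not say that footnote f's publication is the Cincinnati series, nor what race-specific rates it reports. The identity is plausible but unproven. The Ohio comparisons hold without it.

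**Were 2.9 and 7.2 meant to recombine to Cincinnati's 7.2?** The documents do not support that. The white rate comes from Colorado data (16.7 × 0.39/2.20 = 2.96), and Section 4.2.2.4 allows mixed sources. What stands is that two inputs in one table disagree with data the protocol itself reports for one of its centers.

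**Would Charleston support a value much nearer 7.2?** Its 46% type 2 share with type 1 at 13.1 gives 13.1 × 0.46/0.54 ≈ 11. That is circular, because 13.1 derives from footnote f, and Table 2-1 does not mark the Charleston series as incident cases.

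**Does the plan's own prevalence contradict 29-42?** In part. Assume constant incidence and a mean of five years at risk within ages 10-19. Table V-7's 1.18 per 1,000 then implies (1.18 − 0.5)/5, about 14 per 100,000, if 0-9 incidence is the planned 5.0. It implies (1.18 − 0.1)/5, about 22, if 0-9 incidence is what the 0-9 prevalence of 0.05 implies. A rate of 31 would imply about 1.65-2.05 per 1,000. Rising incidence could explain part of the gap. This check also puts 7.2 too low, so the direction stands, but the size is less certain.

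**Is the study less precise than claimed?** No. The error runs the other way. All eligible cases are registered, so no enrolment target depends on this cell.

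**Conclusion.** The concern holds as a conflict between a planning input and the protocol's own data. The 7.2 cannot be reconciled with the Cincinnati figures in Tables 2-1 and 2-2, which point to an African American type 2 rate of about 29-42 per 100,000 at ages 10-19. The stated African American precision is therefore too pessimistic, while expected type 2 counts and the associated workload are too low, chiefly in South Carolina. Overall precision barely moves. Tables 6-1 and 6-3 rest on separate prevalence inputs and are unaffected.

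The size rests on three assumptions: the 69% share (54 cases, 1982-1994) applies to ages 10-19 in 1994; the Cincinnati race mix around 2000-2001 applies to 1994; and a Cincinnati-based rate transfers to the other centers. The totals are provisional because type 1 is held at a figure that itself needs a new source.

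**What to change.** 1. Check which population footnote f's rate covers, and state it in Table V-8.
2. Reconcile Table V-8 with Table 2-1. Replace 7.2 with an African American rate, computed as combined rate × African American case share / African American population share at 10-19. Show a range of about 29-42 with its assumptions, and set it beside the prevalence in Table V-7.
3. Source the African American type 1 rate at 10-19 independently of footnote f. Do not rescale it.
4. Recompute Tables V-4 to V-6, 4-3 and 3-2, and the affected rows of Table 6-2 (overall, ages 10-19, gender and Black), and carry the new annual total wherever 785 is quoted.

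The cost is a source check and recalculation of planning tables. Data collection, eligibility and analysis do not change.

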3.1. CINCINNATI-CINCINNATI CHILDREN'S HOSPITAL MEDICAL CENTER

This Cincinnati center is located in Cincinnati, OH at Children Hospital Medical Center. For both the prevalence and incidence components of the study prevalent and incident cases, children with diabetes who reside in Cincinnati and the eight counties that surround Cincinnati will be identified and invited to participate.

Children's Hospital, established in 1883, is the only pediatric facility serving southwest Ohio, northern Kentucky, and southwest Indiana. As a result children and youth with complex medical problems are referred to Children's Hospital. The diabetes team, established in 1978, has provided care and education for pediatric diabetes patients in the greater Cincinnati area. In 1988, a computer database containing demographic and other data on all patients diagnosed with diabetes since 1978 was established. For SEARCH, the Cincinnati center will use the information in this existing computer database supplemented by prospectively collected data over a four-year period from newly diagnosed patients with childhood diabetes.

Although a majority of the care and management of childhood diabetes is provided at Children's Hospital, in order to insure complete ascertainment the investigators have established a network that identifies, contacts and collects data from the small number of patients with childhood diabetes who are not diagnosed at Children's Hospital.

The Cincinnati center will use the U.S. census as the source of denominator estimates.

In 2000, approximately 550,000 children and youth less than 20 years of age resided in the eight counties surrounding Cincinnati, including about 15% of non-white racial/ethnic background.

3.2. COLORADO-WESTERN REGISTRY OF DIABETES IN YOUTH

The Colorado center is located in Denver at the University of Colorado Health Sciences Center. For the prevalence component of the study, children with diabetes who reside in the urban-suburban counties surrounding Denver (Denver, Adams, Douglas, Jefferson, Boulder), six rural counties in south-central Colorado (Conejos, Costilla, Alamosa, Saguache, Mineral, Rio Grande), Mesa county in western Colorado, and the Navajo Nation Native American reservation in Arizona/New Mexico, the Gila River Pima Indian Reservation in Arizona, and the Apache Indian Reservations White Mountain and San Carlos in Arizona will be asked to participate. For the incidence component of the study, case ascertainment will be expanded to all 63 counties in Colorado, and several additional Native American reservation populations will be approached to participate.

For the prevalence component of SEARCH, the Colorado center will use multiple sources, which are site and area dependent. The types of data sources include: pediatric endocrinologist computerized databases, HMO computerized diabetes registries, diabetes registries based on the Diabetes Electronic Management System (DEMS), school based health clinic charts, primary care practices, computer-stored hospital discharge records, diabetes educators' case records, Indian Health Service computer-stored hospital and ambulatory databases, NIH/NIDDK research databases, and death certificates. For the incidence component of SEARCH, Colorado center will expand its case identification to all of Colorado cases. Cases will be identified using a network of reporting clinics, physicians, and diabetes educators supplemented with information from hospital discharge records and computer-stored data sources.

The Colorado center will use the U.S. census as the source of denominator estimates.

In 2000, approximately 1,400,000 children and youth less than 20 years of age resided in Colorado and the Native American reservations included in the study. About 35% of the children/youth encompassed by the Colorado Center are of non-white racial/ethnic background.

3.3. HAWAII—PACIFIC HEALTH RESEARCH INSTITUTE

The Hawaii center is located in Honolulu, Hawaii at the Pacific Health Research Institute. Partners in this project with the Pacific Health Research Institute (PHRI) at the Hawaii Center will include Kaiser Permanente-Hawaii, the Hawaii Medical Service Association (HMSA), and the State of Hawaii Department of Human Services, Med-QUEST Division. For the prevalence component of the study, children with diabetes who are members the major health plans in Hawaii (the Hawaii Medical Service Association (HMSA), Kaiser Permanente-Hawaii and the State of Hawaii, and Department of Human Services Med-QUEST) in 2001 and reside on Oahu will be asked to participate. For the

incidence component of the study, case ascertainment will be expanded to include members of these three health plans on all the six major islands of Hawaii (Oahu, Hawaii, Maui, Kauai, Molokai and Lanai). The combined membership of these three plans includes over 90% of the state's non-military residential population under age 20 as determined by the US Census.

The Pacific Health Research Institute (PHRI) is a non-profit research institute created in 1960. Since 1996, HMSA and Kaiser Permanente-Hawaii have been contributing data to the Hawaii Diabetes Data Network (HDDN). For the prevalence component of SEARCH, the Hawaii center will use the information in the existing computer database. For the incidence component of SEARCH, cases will be identified using a rapid reporting system of clinics and physicians.

The Hawaii center will use administrative membership databases from the participating health systems as the source of denominator information. Estimates of the number of children in each ethnic group will be made based on the U.S. census with the assumption that the membership of the health plans is representative of the geographic base from which cases are drawn.

In 2000, approximately 300,000 children and adolescents less than 20 years of age resided on the six Hawaiian islands, including approximately 70% Asian and Pacific Islanders. All patients in the state's Medicaid program. (Med-QUEST) will be included.

